1.0. Summary

This proposal, originally submitted to the Cystic Fibrosis Foundation (CFF) Spring 2019, has been changed at the recommendation of the CFF to reflect a retrospective approach to determine safety and efficacy of contraception among up to 625 women of reproductive age with cystic fibrosis (CF). In planning for this retrospective approach, the University of Washington (UW) study team determined that the optimal way to collect contraceptive use data would be through patient self-respondent approach, since the Cystic Fibrosis Foundation Patient Registry (CFFPR) does not collect information on contraception, and electronic medical records (EMR) often have inaccurate information about contraceptive use and do not include over-the-counter (OTC) methods. Given the critical nature of collecting exposure (contraceptive) data for this retrospective approach, the UW study proposed using the first year to pre-test self-respondent questions with up to 50 women with CF. **The purpose of this pilot survey is to determine the best approach to collect reproductive health information due to the sensitive nature of questions on the topics of contraceptive use, pregnancy, and menstruation. We will determine if responses about past contraceptive use are more complete when the survey is administered or when respondents answer questions on their own at home using an online survey.**

Once the pilot phase is complete, we propose to conduct a retrospective observational cohort study of up to 625 women with cystic fibrosis aged 18-45 years at time of enrollment. Participants will be recruited from 10 separate CF centers. Participants will be recruited for the study from their CF center through email, postal service, or in-person contact. CF center research staff will inform interested patients about the study, check that the patient has a CFFPR ID number, and pass along the patient names, email addresses, and CFFPR number to the UW study team who will determine eligibility. If the potential participants meet enrollment criteria, they will be consented on-line, and continue to the online survey that they can complete at home. The self-reported data will be linked with CFFPR objective pulmonary data to examine the association of hormonal contraceptive use on pulmonary health, outcomes related to CF-liver dysfunction (CFLD), nutritional status, and venous/arterial thromboembolism. The UW study team will work with each of the 10 separate CF centers to provide a select number of dual energy X-ray absorptiometry (DXA) scan bone mineral density test scores from their center's EMR, which will be used to validate bone health information in the CFFPR.

2.0. Background/Rationale

Family planning decisions are increasingly important for women with CF as most reach reproductive age in reasonable health. As CF care management and directed therapies advance, the number of women with CF in the US over age 18 has nearly doubled over the last 15 years: from 4,000 to 7,200. The CFF has an existing comprehensive patient registry, the CFFPR, which captures annual data on over 90% of all persons with CF in the US (1). While it is comprehensive regarding most aspects of CF patients' health, the CFFPR currently only asks one question that addresses reproductive health for women over 18 living with CF: "Was the patient pregnant during the reporting year?".

Reliable information is urgently needed to enable healthcare providers to help CF women understand the effectiveness and safety of current contraceptive methods for them. While infertility usually affects men with CF, at least 50% of women with CF are estimated to be physiologically capable of becoming pregnant without fertility treatment (2); however, that percentage is expected to rise with the use of new life sustaining medications, such as the CFTR modulators and especially the newly Food and Drug Administration (FDA)-approved triple-combination modulator, TRIKAFTA® (3).

Our recently completed survey study among 150 women at three CF centers, suggests that only about 60% of reproductive—aged women with CF are using contraception (4). Among those who are, oral contraceptive pills (OCPs) and condoms are the most commonly reported methods. Gaps in quality contraceptive care for women with CF exist, in part because, surprisingly, women with CF prefer to receive their sexual health care within the CF clinics, but many CF providers do not feel prepared to deliver safe and detailed contraception care (5). This information gap is exacerbated by the limited data which exist to inform contraceptive care provision for women with CF. In fact, most studies evaluating contraceptive safety are limited to oral contraceptive pills, even though the number of choices of FDA-

CASE.4.CF Study Protocol

approved contraceptives has increased significantly since 2001, especially with the FDA-approval of hormonal longacting reversible contraceptive methods. In today's U.S. market, two types of hormonal contraceptives exist: estrogenand-progestin-containing methods (a.k.a. combined hormonal methods) and progestin-only methods. Within the estrogen-containing methods, contraceptive choices include oral pills and non-oral methods, such as the transdermal patch and vaginal ring. Within the progestin-only methods, contraceptive choices include four different hormonal intrauterine devices (IUD), a subdermal implant, a 3-month injectable depo-medroxyprogesterone acetate (DMPA), and progestin-only oral pills

The most recent edition of the national contraceptive guidance for women with medical conditions called the United States Medical Eligibility Criteria for Contraceptive Use (USMEC), was released in 2016 by the Centers for Disease Control and Prevention (CDC), which lists CF as a chronic health condition (6). The USMEC lists all hormonal methods safe to prescribe without restrictions (USMEC = 1), except the 3-month injectable, depot-medroxyprogesterone acetate (DMPA). DMPA is listed as USMEC = 2, in which the advantages of using the method in a woman with CF generally outweighs the theoretical or proven risks because of concerns about DMPA on bone health. Despite these national recommendations, the data for women with CF and hormonal contraception are limited. Potential complications for CF patients include decreased pulmonary function, CF-related diabetes (CFRD), CFLD, increased gallbladder disease, decreased nutritional status, increased venous thromboembolism and poor bone health. There are theoretical concerns that hormonal contraception may adversely impact these complications. Another concern is the reduced efficacy of hormonal contraception, specifically oral contraceptive pills with concomitant use of CFTR modulators.

The definitions for normal bone, osteopenia, and osteoporosis are based on bone mineral density (BMD) scores. BMD is measured by dual energy X-ray absorptiometry (DXA), which provides both T-scores and Z-scores. These scores are used to define whether a person is categorized as having osteoporosis, osteopenia, or normal bone. According to the World Health Organization (WHO), the T-score is the number of standard deviations (SD) above (+) or below (-) the mean BMD in a young, normal, sex-matched population and is preferred for postmenopausal women. The Z-score is the number of standard deviations (SD) above (+) or below (-) the mean bone density in a normal, sex- and age-matched population and is preferred in females prior to menopause (7). In contrast to WHO criteria, the CFF uses Z-scores for children less than 18 years, considers T- and Z-scores as nearly equivalent for persons between ages 18-30 years, and uses T-score findings for persons with CF ages 30 years and older (8).

Our project is specifically designed to collect more information on these critically important issues by expanding our pilot contraceptive CFFPR study and further assess the safety and efficacy of contraception among patients with CF. With pilot funding from the Society of Family Planning, Drs. [name], [name], and [name] collaborated with two other CF centers to assess feasibility, data completeness, and data accuracy of a pilot contraceptive registry. Having successfully linked women with CF's self-reported information on current and prior contraceptive use with clinical data information obtained from the CFFPR, we are now ready to expand our work to include seven additional CF Centers for a total of ten centers (see Table 2).

The research questions we aim to answer for women with CF, aged 18-45 years in this retrospective study include:

- (1) Are estrogen-containing or progestin-only hormonal contraceptives associated with improved objective pulmonary symptoms compared to women with CF who use non-hormonal methods (control)?
- (2) Are estrogen-containing or progestin-only hormonal contraceptives associated with increased incidence of CFrelated liver disease (as noted with increasing trend of liver enzyme tests), gallbladder disease or thromboembolism?
- (3) Are estrogen-containing or progestin-only hormonal contraceptives associated with increased serum glucose trends (as measured by oral glucose tolerance testing) compared to women using non-hormonal methods?
- (4) Does hormonal contraceptive use affect nutritional status for women with low body mass index?

- (5) What is the percent agreement between CF Clinic DXA scan T-scores and CFFPR data about osteoporosis, osteopenia and bone fracture?
- (6) Are women who use CFTR modulators and more likely to become pregnant unintentionally while taking hormonal contraception (compared to women on non-hormonal contraception)?
- (7) Does use of hormonal contraception result in a higher proportion of patients with mucoid vs. non-mucoid *Pseudomonas aeruginosa* compared to non-hormonal contraceptive users?

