3.0. Hypothesis

- Estrogen-containing methods, but not progestin-only methods, reduce the annual rate of pulmonary exacerbations, the microorganisms associated with a more rapid decline in lung function, and improve ppFEV1 (or absolute FEV1) of women with CF when compared to women with CF who use non-hormonal contraception (control group).
- Estrogen-containing oral methods of birth control are associated with higher incidence of gallbladder disease (defined as gallstones, requiring surgery), increased liver function enzyme values, and/or increased incidence of thromboembolism among women with CF.
- Both estrogen-containing and progestin-only hormonal methods improve BMI among women with CF, which is linked to nutritional status.
- The strength of agreement between DXA scan T-scores and CFFPR data about osteoporosis, osteopenia and bone fracture will be "substantial."
- The effectiveness of oral birth control is reduced compared to other methods of hormonal birth control in the presence of CFTR modulator use.
- Hormonal birth control use results in a greater proportion of patients with mucoid *Pseudomonas aeruginosa*, in patients who are *P. aeruginosa* positive, compared to non-hormonal contraceptive users.

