4.2. Secondary Study Objectives/Endpoints

- To assess the association of hormonal contraceptive use on trends in lung function (FEV1) over time, compared to non-hormonal contraceptive users (primary control) and non-contraceptive users (secondary control).
- To assess the association of hormonal contraceptive use on the incidence of venous or arterial thromboembolism.
- To assess the association of hormonal contraceptive use on prevalence of liver dysfunction, defined as gallstones (requiring surgery), hepatic steatosis, hepatic cirrhosis, and/or incidence of increased liver enzyme test values (ALT/GGT). Increased liver enzymes is defined as exceeding upper limit of normal on at least 3 occasions over 12-month period.
- To assess the association of hormonal contraceptive use on serum glucose trends, incidence of insulin resistance or time to CF-related diabetes (requiring insulin treatment).

- To assess association of hormonal contraceptive use on nutritional status through the evaluation of BMI trends.
- To validate bone health information in CFFPR with chart data obtained from one CF center (limited due to need for data use agreements between institutions for EMR data).
- To determine if those using hormonal contraception while using CFTR modulators report higher rates of unintended pregnancy compared to those taking non-hormonal contraception.
- To assess proportion of mucoid *P. aeruginosa*, in patients who are *P. aeruginosa* positive, among hormonal contraception users compared to non-hormonal contraceptive users.

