7.2. Eligibility Criteria

The study population will be women with CF who have used any form of contraception for protection against pregnancy or for treatment of dysmenorrhea, pelvic pain, abnormally heavy or prolonged menstrual bleeding, excessive uterine bleeding, endometriosis, acne, or amenorrhea.

Table 4: Full study inclusion and exclusion criteria

Inclusion Criteria
Females ages ≥ 18 and < 46 years at enrollment
Confirmed patients at one of the 10 participating CF centers (has been seen at least one time for a face-to-face
office visit at the CF center in the last 2 years)
CFFPR participant (noted as having a CFFPR ID number)
Has internet access
Has a functioning email addresses or may create a functioning email address at enrollment
Willing to consent to obtain request of their identified data from CFFPR
Willing to consent to their CF center to provide data related to contraceptive medication and DXA scan test results
as far back as 2013 in clinic EMR
Exclusion Criteria
Not in CFFPR
Non-functioning email address
History of organ transplant
Participant in pre-test phase of this study

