Exposure of interest	Outcome	Confounders/Covariates	Rationale
	present or absent as		
	recorded in CFFPR)		
	Nutritional status	CF genotype class	
	Change in BMI	CF-specific vitamins (Fat soluable A, D and E) (defined as	
		present or absent as recorded in CFFPR)	
		Taking any pancreatic enzyme replacement therapy (noted under medications in CFFPR)	
		CFTR modulator use (will stratify by type of modulator)	
	Bone outcomes	Length of oral steroid use	Contributes to bone
	Osteoporosis, fragile bone	(person-months of use)	weakening
	fracture	Comorbidity with pancreatic insufficiency	Reduced Vit D/Calcium absorption
		Exercise	Help prevents osteoporosis
		Age	Known risk factor for osteoporosis
		BMI	Reduced BMI is a risk factor for osteoporosis
		CF genotype class	
		Length of hormonal	1
		contraceptive use (person-year	
		of exposure)	
		Smoking	Known risk factor for osteoporosis

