9.3. Statistical Methods

Because this is a retrospective cohort study, we are most interested in determining whether this exposure (to hormonal contraception) is associated with our primary outcome (counting the number of pulmonary exacerbations requiring additional IV in a given year) and/or our secondary outcomes (new respiratory microbiology, liver disease/non-cirrhosis, gallstone, requiring surgery/procedure, improved BMI, incidence of VTE, osteoporosis and fragile bone fracture). Women on hormonal contraception will be compared to the primary control group of women on non-hormonal contraception. We will also compare to women on no contraception, as the secondary control group. We will exclude persons with these existing diagnosis at the start of the follow up period for outcome data (January 1, 2010). Within this objective we will be able to calculate incidence rates, relative risks and confidence intervals. We will use Poisson regression to calculate progestin-only and combined hormonal method to non-hormonal method pulmonary exacerbation rate ratios and 95% confidence intervals. This allows for adjustment of follow-up time of each individual.

(Objective 1a): We will evaluate lab values over time (ppFEV1%, serum AST, ALT, alkaline phosphatase) to determine if trends between hormonal contraceptive users and non-hormonal contraceptive users differ. See Table 5 for confounders and covariates that we will use to adjust for the primary and secondary outcomes.

We will model ppFEV1 via generalized estimating equations (GEE), allowing for correlation within a subject, and compare via a fixed effect for exposure. Among women who change or stop contraception, we will estimate and compare within-participant difference in outcomes via the model (if numbers allow). We will censor women who switch method types or become pregnant, and for 6 months post pregnancy, for the primary analysis and subsequently follow them to leverage within-patient data and analyze changes in pulmonary status and contraception. Presence of respiratory microbiology will be estimated longitudinally via GEE with a logit link function. Graphic displays and summary statistics will be used; all *p* values will be two-sided.

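### Research question 4 asks about women with low BMI, but nothing later in the plan defines that group or estimates the effect in it

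*Combined protocol and SAP*

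**What the plan says.** Research question 4 (section 2.0) names a restricted population: "Does hormonal contraceptive use affect nutritional status for women with low body mass index". The later sections treat the same topic as follows.

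- **Hypothesis (3.0):** "Both estrogen-containing and progestin-only hormonal methods improve BMI among women with CF, which is linked to nutritional status". No starting BMI is mentioned.
- **Secondary objective (4.2):** "To assess association of hormonal contraceptive use on nutritional status through the evaluation of BMI trends". No subset is named.
- **Eligibility (7.2, Table 4):** the criteria include age, centre, registry membership, email access, consent and transplant history. BMI is not among them.
- **Outcomes (7.5, Table 5):** the nutritional outcome is change in BMI. Its covariates are genotype class, vitamins, pancreatic enzymes and modulator use; baseline BMI is absent. The only stratification named is "CFTR modulator use (will stratify by type of modulator").
- **Statistical methods (9.3):** the list of secondary outcomes contains "gallstone, requiring surgery/procedure, improved BMI, incidence of VTE". What counts as improved is not defined, and no model for BMI is written.
- **Appendix, part IV:** BMI value and BMI percentile are requested from the registry at encounter level.

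**The concern.** The population in the question differs from the population in the hypothesis, objective and outcome table. An effect averaged over all enrolled women is a different quantity from the effect in those who start with low BMI, and one can be present without the other. A reader who follows the plan as written would finish with a result on BMI that does not answer question 4.

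The loss of the restriction does not look like the protocol's usual shorthand. Question 6 is limited to users of CFTR modulators, and both 3.0 and 4.2 keep that condition. The low-BMI condition is not kept.

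The undefined word *improved* in 9.3 adds a second ambiguity. Without a stated direction, threshold or starting point, the analyst must decide after the fact which changes count. If the low-BMI cut-off is also chosen after the registry data are in hand, that choice is open to selection.

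**Working it through.** The documents give no cut-off, share, SD, sample size or power for BMI, so there is no stated figure to reproduce. The check has three parts.

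**1. Does any passage restore the restriction?** Sections 3.0, 4.2, 7.2, 7.5 and 9.3 were compared with question 4. None defines low BMI, plans a subgroup or interaction, or adjusts the nutritional outcome for baseline BMI. The one baseline selection rule in 9.3 is "We will exclude persons with these existing diagnosis at the start of the follow up period for outcome data (January 1, 2010"). It removes women with existing diagnoses and does not select women with low BMI.

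**2. Can an all-women contrast answer question 4?** Let *s* be the share of women with low BMI, *d_L* the effect in them and *d_O* the effect in all others. If the share is the same in each exposure group, then

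pooled effect = *s*·*d_L* + (1 − *s*)·*d_O*.

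One equation has two unknown effects. Both effect sizes and the share below are assumed, for illustration only:

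| Share *s* | *d_L* = 1.0, *d_O* = 0 (kg/m²) | *d_L* = 0, *d_O* = 0.5 (kg/m²) |
|---|---|---|
| 10% | 0.10 × 1.0 = 0.10 | 0.90 × 0.5 = 0.45 |
| 30% | 0.30 × 1.0 = 0.30 | 0.70 × 0.5 = 0.35 |

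At a 30% share, opposite answers to question 4 give nearly the same pooled result (0.30 and 0.35). At 10%, the larger pooled result comes from the case with no effect in low-BMI women. The women in *d_O* include those of normal weight, so the table says nothing specific about overweight women.

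**3. How precise would a low-BMI estimate be?** Inputs from section 7.7 are 575 enrolled, 15% attrition, alpha 0.05 and about half on hormonal methods. Section 9.3 makes tests two-sided. The 1:1 split, 80% power and the shares are applied here as assumptions.

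- Analysable women: 575 × 0.85 = 489, or 244.5 per group.
- Minimum detectable difference (MDD) in SD units: (1.960 + 0.842) × √(2/n), with n per group.
- Power in the subset for an effect that the full cohort detects with 80% power: Φ(2.802 × √s − 1.960).

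| Share | n per group | MDD (SD) | Power in subset |
|---|---|---|---|
| All women | 244.5 | 0.25 | 80% |
| 30% | 73 | 0.46 | 34% |
| 20% | 49 | 0.57 | 24% |
| 10% | 24 | 0.80 | 14% |

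These figures treat the subset as a stand-alone comparison of two equal groups. Separate estrogen-containing and progestin-only contrasts, or a non-hormonal group smaller than half, would be less precise.

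**The case against.** **Question 4 may be the outlier.** The hypothesis, objective and outcome table agree with one another, and only question 4 names low BMI. Rewording question 4 would remove the contradiction just as well. This stands: the documents show that the passages must be reconciled, not which population the sponsor intends.

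**The outcome may not be one-directional.** A reader might infer that the plan counts any rise in BMI as nutritional benefit, so that weight gain in an overweight woman scores as success. That inference draws some support from the hypothesis, and Table 5 does treat BMI of 30 or more as a thromboembolism covariate and obesity as contributing to liver dysfunction. But the documents do not state such a rule. Section 4.2 speaks of trends and Table 5 of change, both neutral in direction; tests are two-sided; and no passage defines *improved* as any increase. What remains is a missing definition.

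**No pooled BMI model is written.** A reader might also infer that 9.3 prescribes a pooled BMI analysis. It gives models for exacerbations, ppFEV1 and microbiology, but none for BMI. The supportable statement is that no restriction, subgroup or interaction is specified.

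**The plan is to be refined.** Sections 6.0 and 7.7 say that the analysis plan will be developed further during the pilot. That is an opportunity to correct the point, but it sets no population or cut-off.

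**The subset is small.** This stands, as the working shows. It argues for estimation with an interval and for keeping the all-women analysis; it does not argue for leaving the question unaddressed.

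**Conclusion.** The inconsistency is established from the text alone and needs no assumption: question 4 is limited to women with low BMI, and no later section defines, selects or separately estimates that group. As planned, question 4 goes unanswered.

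The size of any resulting error in BMI units cannot be given, because the documents contain neither the low-BMI share nor an expected effect. The pooled values in the working only illustrate that the two quantities can differ. The precision figures rest on an assumed 10–30% share and a 1:1 split of 489 analysable women.

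This affects one of eight secondary objectives and leaves the primary outcome untouched. It should be corrected, and correction is cheap because the BMI data are already on the request list.

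**What to change.** The sponsor should first state which population question 4 concerns.

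If low-BMI women are meant, change 4.2 and 9.3 as follows:

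1. Keep the analysis of BMI change in all women.
2. Add a prespecified baseline-BMI-by-exposure term. Report from it the exposure effect in women below a low-BMI cut-off, with its interval. The sponsor chooses the cut-off and records it before the registry data are received; the Appendix places that request after recruitment is complete. The same cut-off applies to every exposure group.
3. Define baseline BMI as the last registry value at age 18 or over, at or before the start of the analysed exposure period. For women already exposed by the time of their first adult value, use that first adult value and exclude these women in a sensitivity analysis.
4. In 9.3, write *change in BMI*, as Table 5 does, in place of *improved BMI*.

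Step 3 matters because the first registry value in follow-up would be a poor baseline. Table 4 admits "Females ages ≥ 18 and < 46 years at enrollment", and enrolment follows pre-testing that ends in July 2020, while outcome follow-up starts in January 2010. The gap is about 10.5 years, so a woman younger than about 28 at enrolment was under 18 when follow-up began. Table 3 plans 383 of 575 women aged 18–35, although it does not show how many are under 28. A single adult cut-off does not carry the same meaning for childhood values. Exposure is also asked about from 2008, so a first value from 2010 may come after hormonal use began.

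If all women are meant, reword question 4 to match the objective; step 4 still applies.

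The cost is SAP wording and one extra model term on data already requested. The downside is an imprecise low-BMI estimate, so a non-significant result there should not be read as showing no effect.
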